Figure 1 presents the precision of the overall VE for total sample sizes (cohort sizes) varying from 1,000 to 50,000 subjects, when assuming a true VE of 50%, an influenza attack rate in the unvaccinated of 5% and a total vaccination coverage of 5%, 20%, 50% and 70%. The calculations are based on an anticipated true VE of 50% as this is a conservative choice, requiring larger sample sizes compared to assuming lower/higher VE values. A cohort study based on 5000 subjects will result in 95% CIs of the overall VE with a lower limit larger than 25% given a true VE of 50% and an influenza attack rate of 5%, for coverages of >20%.

[figure not shown]
[figure not shown]
[figure not shown]

Figure 1. Precision of the overall VE expressed as the lower limit of the 95% CI, assuming a true VE of 50% (indicated with the black horizontal line), an attack rate in the unvaccinated of 5% and a total vaccination coverage of 5%, 20%, 50% and 70%.

[figure not shown]
Figure 2 presents the precision of the brand-specific VE for total sample sizes (cohort sizes) varying from 1,000 to 50,000 subjects for the same parameter settings as above and additionally assuming the brand of interest accounts for 10%, 20%, 40%, 60%, 80% and 90% of the total vaccination coverage. A cohort study based on 5000 subjects will result in 95% CIs of the brand-specific VE with a lower limit larger than 25% given a true VE of 50% and an influenza attack rate of 5%, for brands covering 40% to 90% of the influenza vaccines when the overall vaccination coverage is 50% or more.

[figure not shown]
a) Total coverage: 5%

b) Total coverage: 20%

c) Total coverage: 50%

d) Total coverage: 70%

Figure 2. Precision of the overall VE expressed as the lower limit of the 95% CI, assuming a true VE of 50% (indicated with the black horizontal line), an attack rate in the unvaccinated of 5%, a total vaccination coverage of 5%, 20%, 50% and 70% and that the brand of interest accounts for 10%, 20%, 40%, 60%, 80% and 90% of the total vaccination coverage.

Data management

Each study site is responsible for the data collection, data validation, and data management of their individual study. DRIVE has developed a generic data management plan (task 4.2.1) and set up the necessary infrastructure for data collection and analysis of the pooled data (task 4.2.2).

- *Each study site to specify how data are collected and validated.*
- *Each study site to specify procedures of data management.*

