Annex 3: Sample size considerations for cohort studies

Authors: [name] and [name]

For questions or feedback, please contact

e-mail: [contact]

This document provides sample size estimations for estimating overall and brand-specific influenza vaccine effectiveness (VE) using the cohort design. The minimal detectable VE as well as precision estimates are provided for various parameter settings and recommendations are formulated.

Minimal detectable vaccine effectiveness

The minimal detectable VE is the smallest VE that can be detected as significantly greater than zero in a given study using hypothesis testing. The minimal detectable VE for a cohort study is estimated as

$$VE_{MD} = 1 - RR_{MD(RR<1)}, \quad (1)$$

where $RR_{MD(RR<1)}$ is the minimal detectable relative risk (RR) if $RR < 1$, or

$$RR_{MD(RR<1)} \cong \frac{1}{2a} \left(b - \sqrt{b^2 - 4ac} \right), \quad (2)$$

where

$$a = Y + \pi Z; \quad b = 2Y + Z; \quad c = Y - r(1 - \pi)Z,$$

in which

$$Y = rN\pi^2; \quad Z = (r + 1)\pi \left(z_{\frac{\alpha}{2}} + z_{\beta} \right)^2$$

for attack rate in the unexposed π , exposed to unexposed ratio r with $r = \gamma/(1 - \gamma)$ with coverage γ , total sample size N , and where z_{α} and z_{β} are the standard normal z-score for the type I and type II error rates (Woodward 2013).

We calculated the minimal detectable overall VE (1) with 80% power ($1 - \beta$) and a two-sided 95% confidence coefficient ($1 - \alpha/2$) for cohort studies with the total number of subjects varying from 1000 to 50000, while assuming overall vaccination coverages of 5%, 20%, 50% and 70% and an attack rate of 5% and 15% in the unvaccinated.

We additionally calculated the minimal detectable brand-specific VE, where subjects are considered exposed when they were vaccinated with the brand of interest and unexposed when they were unvaccinated during the study's follow-up. This means that the same comparator group of unexposed subjects is used for the different brand-specific estimates. The minimal detectable brand-specific VE is calculated for the same settings above, additionally assuming that the brand of interest accounts for 10%, 20%, 40%, 60%, 80% and 90% of the overall vaccination coverage.

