[figure not shown]
$$A_0 = N * (1 - \gamma) * AR$$

$$N_1 = N * \gamma$$

[figure not shown]
$$N_0 = N * (1 - \gamma)$$

We calculated precision of the overall VE based on a two-sided 95% CI for cohort studies with the total number of subjects varying from 1000 to 50000, whilst assuming overall vaccination coverages of 5%, 20%, 50% and 70%, VE of 20%, 50% and 70%, and an attack rate in the unvaccinated of 5% and 15%. To calculate the precision of the brand-specific VE, we additionally assumed that the brand of interest accounts for 10%, 20%, 40%, 60%, 80% and 90% of the overall vaccination coverage

[figure not shown]
The results for precision of the overall VE assuming attack rates in the unvaccinated of 5% and 15% are given in Figures 4 and 5, respectively. These figures represent precision by total sample size. The results for the precision of brand-specific VE for anticipated true VE of 20%, 50% and 70%, and 5% attack rate are given in Figures 6 to 8.

a) 20% VE

b) 50% VE

c) 70% VE

Figure 4. Precision of overall VE for a cohort study assuming vaccination coverage of 5%, 20%, 50% and 70%, VE of 20%, 50% and 70% (indicated with the black horizontal line), and 5% attack rate in the unvaccinated, by total sample size.

[figure not shown]
[figure not shown]
[figure not shown]

[figure not shown]
Figure 5. Precision of overall VE for a cohort study assuming vaccination coverage of 5%, 20%, 50% and 70%, VE of 20%, 50% and 70% (indicated with the black horizontal line), and 15% attack rate in the unvaccinated, by total sample size.

[figure not shown]
a) 5% overall coverage

b) 20% overall coverage

[figure not shown]

c) 50% overall coverage

[figure not shown]

d) 70% overall coverage

[figure not shown]
Figure 6. Precision of brand-specific VE for a cohort study assuming an anticipated true VE of 20% (indicated with the black horizontal line), overall vaccination coverage of 5%, 20%, 50% and 70% with the brand of interest covering 10%, 20%, 40%, 60%, 80% and 90% of the overall coverage, and 5% attack rate in the unvaccinated, by total sample size.

[figure not shown]
a) 5% overall coverage

b) 20% overall coverage

[figure not shown]

c) 50% overall coverage

[figure not shown]

d) 70% overall coverage

[figure not shown]

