Figure 7. Precision of brand-specific VE for a cohort study assuming an anticipated true VE of 50% (indicated with the black horizontal line), overall vaccination coverage of 5%, 20%, 50% and 70% with the brand of interest covering 10%, 20%, 40%, 60%, 80% and 90% of the overall coverage, and 5% attack rate in the unvaccinated, by total sample size.

[figure not shown]
a) 5% overall coverage

b) 20% overall coverage

c) 50% overall coverage

d) 70% overall coverage

Figure 8. Precision of brand-specific VE for a cohort study assuming an anticipated true VE of 70% (indicated with the black horizontal line), overall vaccination coverage of 5%, 20%, 50% and 70% with the brand of interest covering 10%, 20%, 40%, 60%, 80% and 90% of the overall coverage, and 5% attack rate in the unvaccinated, by total sample size.

Concluding remarks and recommendations

We make the following observations and recommendations based on our sample size calculations for single-site cohort studies;

- We recommend cohort studies based on 5000 subjects or more. A cohort study with 5000 subjects will result in a minimal detectable overall VE of 30-40% for an influenza attack rate of 5% and coverages >20%.
- A cohort study based on 5000 subjects will result in minimal detectable brand-specific VE of 30-40%, for an influenza attack rate of 5% and brands covering 40% to 90% of the influenza vaccines when the overall vaccination coverage is 50% or more.
- A cohort study with a total sample size of 20.000 will result in a minimal detectable VE of 18-20% for an influenza attack rate of 5% and overall vaccination coverages of 20% or more. Improvements in accuracy both in terms of minimal detectable VE and precision will be minimal when increasing sample sizes further.
- In case higher influenza attack rates (+15%) would be expected, lower sample sizes are needed to obtain VE estimates with acceptable precision.
- In case the VE is expected to be low (< 20%), higher sample sizes are required to obtain VE estimates with acceptable precision.
- In case interest is in VE within subgroups, the sample size calculations should be done with respect to the subgroup-specific sample size.
- **IMPORTANT:** These are recommendations to support the design of cohort studies on (brand-specific) influenza VE. Obtaining a minimum sample size is not a requirement for study participation.

References

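### The brand-specific precision claim for 5000 subjects fails at its own boundary (23.7%, not above 25%) and at high coverage; the minimal detectable VE range needs bounds and a caveat on formula (2)

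*Combined protocol and SAP*

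**What the plan says.** The main protocol, in Sample size considerations (text introducing Figure 2), says that a cohort of 5000 yields "95% CIs of the brand-specific VE with a lower limit larger than 25% given a true VE of 50" per cent. It attaches three conditions: a 5% attack rate, a brand share between 40% and 90%, and a coverage condition worded "when the overall vaccination coverage is 50% or more".

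Annex 3, Concluding remarks and recommendations, makes the companion statement about a cohort of the same size, which "will result in minimal detectable brand-specific VE of 30-40%, for an influenza attack rate of 5% and brands covering 40% to 90" per cent of the vaccines used, again for coverage of at least 50%. The power basis is given under Minimal detectable vaccine effectiveness: "We calculated the minimal detectable overall VE (1) with 80% power", with two-sided 5% significance, and the same settings are carried over to the brand-specific case.

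Two definitions fix the calculation. The comparator is stated: "subjects are considered exposed when they were vaccinated with the brand of interest and unexposed when they were unvaccinated during the study's follow-up". The grid is stated under Precision: "we additionally assumed that the brand of interest accounts for 10%, 20%, 40%, 60%, 80% and 90% of the overall vaccination coverage", crossed with overall coverages of 5%, 20%, 50% and 70%.

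**The concern.** The boundary values in the sentence, 40% share and 50% coverage, are themselves grid points, so the claim can be checked directly with the plan's formula. That corner has the smallest brand group of any evaluated setting in the claimed range. The wording also has no upper limit on coverage, although the unvaccinated comparator shrinks as coverage rises.

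The MDVE raises a separate question. Formula (2) is built on the risk difference. The effect measure (1 − RR), the planned logistic, Poisson and Cox models, and formula (3) all work on a ratio scale, so the stated 80% power need not carry over.

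Brand-specific VE is the primary objective, and this generic protocol is the template that sites adapt from 2018/19. A sentence that is wrong here will be copied into site protocols.

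**Working it through.** **Inputs.** N = 5000, attack rate (AR) 5%, true VE 50%, two-sided 95% interval (Sample size considerations; Annex 3, Precision). Coverage g is 50% or 70% and brand share s is 40, 60, 80 or 90%: eight evaluated settings inside the claim. From the comparator definition, N1 = N·g·s and N0 = N·(1 − g); vaccinees of other brands are in neither group.

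**Precision, formula (3).** Lower limit = 1 − RR·exp(1.96·SE), with SE = √(1/A1 − 1/N1 + 1/A0 − 1/N0), A1 = N1·AR·(1 − VE), A0 = N0·AR.

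At 50%/40%: N1 = 1000, N0 = 2500, A1 = 25, A0 = 125.

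- SE = √(0.0400 − 0.0010 + 0.0080 − 0.0004) = √0.0466 = 0.2159
- Lower limit = 1 − 0.5·exp(1.96 × 0.2159) = **23.7%**

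**MDVE, formulas (1)–(2)**, with r = N1/N0, N = N1 + N0 and (1.960 + 0.842)² = 7.849. At 50%/40%:

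- r = 0.4, N = 3500, Y = 0.4 × 3500 × 0.0025 = 3.5, Z = 1.4 × 0.05 × 7.849 = 0.5494
- a = 3.5275, b = 7.5494, c = 3.5 − 0.4 × 0.95 × 0.5494 = 3.2912
- RR = (7.5494 − √(56.993 − 46.439)) / 7.055 = 0.610, so MDVE = **39.0%**

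| Coverage | Share | N1 / N0 | Lower limit, (3) | MDVE, (2) |
|---|---|---|---|---|
| 50% | 40% | 1000 / 2500 | **23.7%** | 39.0% |
| 50% | 60% | 1500 / 2500 | 28.4% | 35.4% |
| 50% | 80% | 2000 / 2500 | 31.0% | 33.2% |
| 50% | 90% | 2250 / 2500 | 31.9% | 32.4% |
| 70% | 40% | 1400 / 1500 | 25.8% | **40.5%** |
| 70% | 60% | 2100 / 1500 | 29.3% | 38.0% |
| 70% | 80% | 2800 / 1500 | 31.2% | 36.6% |
| 70% | 90% | 3150 / 1500 | 31.8% | 36.1% |

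Seven of eight settings reproduce each claim. The precision claim fails at 50%/40%. The MDVE claim is exceeded at 70%/40%, by half a point.

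**What would restore 25%** at that corner: a share of about 44% (45% gives 25.2%), a coverage of about 58% with the 40% share, or N of about 5,445.

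**Coverage beyond the grid but inside the wording.**

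| Coverage | Lower limit, (3) | MDVE, (2), shares 40–90% |
|---|---|---|
| 80% | 24.8% at 40% share | 41.7–44.9% |
| 90% | 19.3–23.3% for shares 40–90% | 56–58% |

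**What formula (2) is.** At its own MDVE for 50%/40%, p0 = 0.05 and p1 = 0.05 × 0.6096 = 0.03048. The difference divided by its unpooled standard error is 0.01952 / √(0.03048 × 0.96952/1000 + 0.05 × 0.95/2500) = 0.01952 / 0.006968 = 2.80. That equals 1.960 + 0.842, so power is exactly 80% for an unpooled risk-difference test.

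**Power for other tests at that MDVE.** Simulated 2×2 tables, 400,000 per setting; each range covers Wald log-RR, Wald log-OR, score and Poisson likelihood-ratio tests.

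| Coverage/share | Brand : unvaccinated | Power (nominal 80%) |
|---|---|---|
| 50%/40% | 0.40 | 73–75% |
| 50%/60% | 0.60 | about 77% |
| 50%/90% | 0.90 | 79–80% |
| 70%/40% | 0.93 | 79–80% |
| 70%/60% | 1.40 | 81–82% |
| 70%/90% | 2.10 | 82–84% |

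At 50%/40%, simulated power reaches 80% at a VE of about 41–42%. The pooled two-proportion (score-type) formula gives 41.7% there, 40.8% at 70%/40% and 32.7% at 50%/90%.

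**The case against.** The shortfall is 1.3 points (25 − 23.7) at one corner of the grid. Both the main text and Annex 3 say the figures are recommendations and that a minimum sample size is not a condition of participation. The Objectives section concedes that a single study may not be powered alone, and the design relies on pooling. All of that stands. It limits the consequence and leaves the 5000-subject recommendation intact, but it does not make the sentence true.

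Annex 3 also discloses formula (2) and defines the MDVE only by reference to hypothesis testing. Using it for planning curves is a choice of approximation, not an arithmetic error. That stands too, which is why a note would suffice.

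A different comparator does not rescue the precision claim. Putting all 4000 non-brand subjects in the comparator still gives 24.7%. Only splitting all 5000 between the brand and the unvaccinated gives a pass (28.8%), and that conflicts with N being described as the total cohort size.

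Three stronger readings are tempting and should be resisted:

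- **That the MDVE claim also fails at 50%/40%.** Under the plan's own formula it does not (39.0%).
- **That formula (2) overstates power in general.** It does so when brand vaccinees are fewer than the unvaccinated, is about right near 1:1, and is conservative when they are more numerous.
- **That the MDVE at 50%/40% should be 44%.** Solving with formula (3)'s standard error gives 43.7%, but simulated power there is already about 84–85%. That would replace an optimistic approximation with a pessimistic one.

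**Conclusion.** The precision statement is wrong as written: 23.7% at its stated boundary, and below 25% at high coverage, including every share examined from 40% to 90% at 90% coverage. The MDVE statement is sound on the evaluated grid apart from a rounding-size excess at 70%/40%, but it too fails once coverage reaches 80%. High coverage is foreseeable. The Background cites a 75% target for the elderly and risk groups, and at 75% coverage with 40% share formula (2) already gives 42.2%.

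The power caveat is conditional. It amounts to about 5–7 points at 50%/40% and about 3 points at 50%/60%, and it reverses at 70% coverage with shares of 60–90%.

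These results assume the stated AR and VE, the unvaccinated-only comparator, and unadjusted two-group comparisons. The plotted curves were not available, so this concerns the text and formulas only. It is a correction of stated figures, with no bearing on whether 5000 is a reasonable recommendation.

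**What to change.** 1. In Sample size considerations, either restate the lower limit as above about 23%, or keep 25% and set the share boundary at 45%.
2. There and in the Annex 3 concluding remarks, replace the open-ended coverage condition with the coverages evaluated, 50% and 70%. Neither option in item 1 is true without this: at 90% coverage a 45% share gives only 20.1%.
3. For the brand-specific MDVE, either restate it as about 32–42% from simulation or a score-type calculation, or keep formula (2) and add a note. The note should say that it is a risk-difference approximation, optimistic when the brand group is smaller than the unvaccinated group. If formula (2) is kept, the upper end should still read about 41% to cover 70%/40%.
4. If the MDVE is recomputed, regenerate Annex 3 Figures 1–3.

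The cost is a few edited sentences and, for the recomputation, one rerun of the sample size calculations. No design element changes.

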- *Each study site to describe the source population and definition of the study cohort Each study site to specify the target groups for which influenza vaccination is recommended, which vaccines are used in the database catchment area, and how the choice of vaccine brand happens*

Study period

The study follow-up will start before the seasonal influenza vaccine is available and before the influenza virus circulation begins in the country/region, to ensure that all vaccinations and all outcomes in the defined cohort are captured. If only aggregated data will be collected that does not allow the shortening of the study subjects' follow-up as part of the statistical analysis, the follow-up may be restricted to the time the vaccine first becomes available or the virus circulation starts, whichever occurs first. The study period will finish at the end of the influenza season.

- *Each study site to specify the study period: the definition of the beginning and end of the study period*
- *Each study site to specify the early, middle and end of the influenza epidemic at the study site according to the information provided by the local influenza surveillance system.*

For the pooled analysis, a harmonised minimum period will be defined (e.g. from week 40 till week 20), but if needed, it will be extended to fully cover the vaccination campaign and the epidemic in each study site. Definition of shorter time periods (e.g. early, middle and end season) will be developed to take into account differences in influenza activity over time and probable development of immunity in unvaccinated population through encounters with the circulating viruses

For addressing the secondary objective of estimating influenza vaccine effectiveness over several seasons, multiple study periods will be combined. If possible, the information from the local surveillance systems of major circulating strains in the study regions will be considered in the analysis. The details of the analysis will be described in the generic study site level SAP.

Study population and follow-up

Cohort of interest

The study cohort comprises the characterised by place of residence, or catchment population of a health care service providing the relevant information for the analyses. The databases may also be characterised by or restricted to e.g. age, or medical, physiological or occupational conditions (e.g. pregnancy, health care workers, other risk/target groups).

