Thus, each study subject may contribute to the follow-up time (person time) as unvaccinated, as partly vaccinated and as vaccinated, according to the definitions in section Exposure, Definition of vaccination status.

Disease episode

Repeated influenza infections during a season are extremely rare, and the first influenza infection affects the probability of the second one. Thus, for specific outcomes, only the first record is considered. However, in addition to the date of the laboratory test for positive influenza finding, the outcome date may be defined as a few days before the test as a proxy for the symptom onset, e.g. for sensitivity analysis.

Instead, there may be repeated visits because of reasons compatible with the non-specific outcomes, e.g. primary care visits before hospitalisation. Outcome-specific definitions for a disease episode will be needed to define the vaccination status at the time of the onset of the disease episode and to indicate which outcome measures are considered to belong to the same disease episode. Outcome-specific definitions for a disease episode are included in the generic site-specific statistical analysis plan (SAP) (Annex 2), to allow harmonization between the individual site-specific analysis plans.

Demographics and baseline characteristics

The baseline characteristics of the study cohort will be described and tabulated by exposure status at the end of the individual follow-up. The association between the baseline characteristics and the exposure status will be investigated using the Fisher's exact test (in case of nominal variables for the baseline characteristics), Mann-Whitney test (in case of ordinal or non-normal continuous variables) or Student's t-test (in case of normal variables). The description of the baseline characteristics will be stratified by the vaccination status at the end of the follow-up and by most important outcome(s) (e.g. laboratory confirmed influenza cases versus others). The proportion of positive influenza tests of all obtained tests will be described, if available.

Measure of effect

The crude (or unadjusted) brand-specific IVE will be estimated as

$$VE = (1 - RR) \times 100\%,$$

where RR denotes the relative risk (ratio of probabilities) or rate ratio (ratio of incidence or hazard rates) of the outcome n for vaccinated individuals versus unvaccinated individuals. The 95% confidence intervals will be calculated as well.

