The analysis must be conducted for each exposure and outcome of interest separately. Confounder-adjusted brand-specific, type specific or overall IVE estimates will be obtained from multivariable regression models, regressing the health outcomes of interest on exposure status, age, sex and the confounders of interest. In case of effect modifiers, an interaction term between exposure and the effect modifier will be included in the regression model or stratified regression analyses will be performed.

Depending on the type of data available, the analytical method(s) will be described in the generic study site level SAP and in a study-specific SAP before the start of the study period. For the outcome of interest, irrespective of its type, multivariable logistic regression will be used, if only the number of events as vaccinated and unvaccinated by number of subjects vaccinated and unvaccinated at the end of the follow-up is known. If the number of events by person time and vaccination status can be assessed, Poisson regression will be used. In case of time-to-event data, Cox regression (proportional hazards) will be used.

Missing data

The cohort should be defined so that the missing data is minimised: the cohort should cover all subjects targeted, especially for the vaccination, and only those subjects. Especially the outcome should be caught non-differentially, i.e. similarly for vaccinated and unvaccinated (see section Study population and follow-up; Cohort of interest). Missing data for events occurring during the follow-up is not available, since 'no record' means by definition 'no event' (unless also the negative

outcome information, e.g. negative influenza tests are available, when a nested case control analysis could be performed).

Missing data may be present, if historical data for background factors at start of the follow-up is not available, e.g. if the subject has moved into the attachment area of the database recently, or it is incomplete, e.g. only part of the databases used in defining the different background factors are available. This subcohort may be excluded from the adjusted analyses.

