Annex 2: Generic study site level Statistical Analysis Plan (SAP)

After analysing the characteristics and structure of the databases used by the participating study sites, a generic study site level statistical analysis plan (SAP) will be developed, including instructions and/or alternatives for defining and harmonising the study variables, including those used for adjusting for potential confounders and effect modifiers, like chronic conditions.

This study site level SAP will be updated annually before the start of the study period, according to experience of the collaboration, to availability of data in participating study sites, and perhaps to predicted features of the upcoming epidemic. This study site level SAP will also be used for updating the Study dataset (Annex 1), if needed.

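### Where vaccine brand is set by practice, municipality or institution, the planned brand-specific confidence intervals make no allowance for clustering, and the dataset has no code for that unit

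*Combined protocol and SAP*

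**What the plan says.** Under Statistical analysis, Measure of effect, the protocol defines VE as one minus a risk or rate ratio and adds: "The 95% confidence intervals will be calculated as well". It names no variance estimator. The model depends on the data a site holds:

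- Counts only: "multivariable logistic regression will be used".
- Person-time: "If the number of events by person time and vaccination status can be assessed, Poisson regression will be used".
- Event times: "In case of time-to-event data, Cox regression (proportional hazards) will be used".

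The adjusted models are described as "regressing the health outcomes of interest on exposure status, age, sex and the confounders of interest", with no term for the practice, municipality or institution.

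On brand, Study setting asks each site to specify "which vaccines are used in the database catchment area, and how the choice of vaccine brand happens". It does not say at what level the choice is made. On the outcome, the section on laboratory-confirmed influenza says that swabbing will usually follow local clinical habit, so recorded incidence can differ between units for reasons beyond transmission.

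Annex 1 has region in the minimum dataset and a yes/no flag for institutional residence. It has no code for practice, municipality, provider or institution. Further detail is deferred: "the analytical method(s) will be described in the generic study site level SAP and in a study-specific SAP". Annex 2, which is to hold the generic site-level plan, states only that "a generic study site level statistical analysis plan (SAP) will be developed".

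**The concern.** The usual standard errors from these three models treat subjects as independent. That fails for a brand contrast when two things hold together: recipients of a brand are concentrated in certain units, and recorded incidence varies between those units. The log rate ratio then carries a between-unit component that the model-based variance leaves out.

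Brand-specific VE heads the primary objective. Intervals that are too narrow can make a difference between local epidemics, or between local testing habits, look like a precisely estimated good or poor brand. If the two-stage pooling weights sites by inverse variance, a site with an understated variance also gets too much weight. That second effect is an assumption, because the pooling plan (DRIVE D4.4) is not part of these documents.

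**Working it through.** **Inputs from the documents.** True VE 50%, attack rate 5% in the unvaccinated, coverage 50%, brand share 40% of vaccines, unvaccinated comparator, cohort sizes 1,000 to 50,000 (Sample size considerations; Annex 3).

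**Assumed inputs.** The SD s of log incidence between units is taken as 0.2, 0.3 or 0.5. In the extreme case each unit uses a single brand, and the brand of interest is used in 40% of units. The documents give no figure for either.

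**The plan's own precision figure.** Formula (3) in Annex 3 treats subjects as independent. At N=5000: N1=1000, N0=2500, A1=25, A0=125.

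- Variance of log RR = 1/25 - 1/1000 + 1/125 - 1/2500 = 0.0466, so SE = 0.216.
- Lower limit = 1 - 0.5 × exp(1.96 × 0.216) = 23.7%.

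The protocol states a limit above 25% for brand shares of 40-90% at coverage of 50% or more. At coverages of 50% and 70% and shares of 40, 60, 80 and 90%, seven of the eight combinations exceed 25%; this one misses slightly. That is a separate matter. What counts here is that the formula has no clustering term.

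**Adding the between-unit component.** Take K units of m subjects, with the brand in K1 = 0.4K of them and unvaccinated subjects in all K. Let w = exp(s²) - 1 be the relative variance of unit incidence: 0.041, 0.094 and 0.284 for s = 0.2, 0.3 and 0.5.

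- Omitted variance of log RR ≈ w × (1/K1 - 1/K) = 1.5w/K.
- Model variance = 1/A1 + 1/A0, with A1 = 0.005Km and A0 = 0.025Km, so 240/(Km).
- True over model variance = 1 + (1.5w/K)/(240/(Km)) = 1 + w·m/160.
- True coverage of the nominal 95% interval ≈ 2Φ(1.96/√ratio) - 1.

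K cancels: under these inputs the ratio depends on unit size, not on the number of units.

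| Units × size | N | Variance ratio (s = 0.2 / 0.3 / 0.5) | Coverage by formula |
|---|---|---|---|
| 50 × 100 | 5,000 | 1.03 / 1.06 / 1.18 | 94.7 / 94.3 / 92.9% |
| 500 × 100 | 50,000 | 1.03 / 1.06 / 1.18 | 94.7 / 94.3 / 92.9% |
| 50 × 1000 | 50,000 | 1.26 / 1.59 / 2.78 | 92.0 / 88.0 / 76.1% |
| 200 × 1000 | 200,000 | 1.26 / 1.59 / 2.78 | 92.0 / 88.0 / 76.1% |
| 100 × 2000 | 200,000 | 1.51 / 2.18 / 4.55 | 88.9 / 81.6 / 64.2% |

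**Simulation.** Log-normal unit effects gave coverage of 91-93%, 88-89% and 75-76% at 50 × 1000, and 96 / 95 / 93% at 50 × 100. A separate simulation with gamma unit effects (relative variance 0.05 and 0.25) gave 92.0% and 77.7% at 50 × 1000, and 94.5% and 93.4% at 50 × 100. In that simulation the lower limit reflecting the true spread at N=50,000 was 41.8% to 37.9%, against 42.8% from formula (3).

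**Brand not segregated.** If brand is mixed evenly within units, K1 = K and the omitted term is zero. Simulated coverage was then 94.5% to 96.6%. If half the brand's recipients are confined to the 40% of units and half are spread evenly, the omitted term is a quarter of its full value. At 50 × 1000 with s = 0.5 the ratio is 1 + 1.775/4 = 1.44 and coverage about 90%.

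**Remedy.** Cluster-robust intervals covered about 93-95% with 50 or more units. With 10 units the uncorrected robust interval covered only 87-88%, so few units call for a small-sample correction.

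**The case against.** The strongest reply is that this is a generic template. The methods are explicitly left to later plans, Annex 2 is a declared placeholder, and Annex 1 may be updated from it. Sites hold their own data, so nothing stops one from clustering on a local code; and region is already a required field, which suffices where brand is set regionally. At the recommended 5000 subjects in units of 100, the loss of coverage is small.

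All of that stands. It makes this an omission in a harmonising document rather than a wrong method laid down. It does not remove the point: the model families are already named, no text directs the later plans to consider clustering, and the dataset offers no code where brand is set below region.

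A reader might go further in three ways, and the documents do not support any of them:

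- **That brand is known to be chosen locally, so the intervals are too narrow in general.** Study setting only asks how the choice is made, and evenly mixed brands cause no under-coverage.
- **That large registers are worse as such.** Going from 50 to 200 units of 1000 leaves the ratio unchanged; larger units raise it.
- **That the variance could not be corrected at all.** A site with its own unit code could do so now.

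**Conclusion.** The point holds conditionally. The plan makes no allowance for within-site correlation, and Annex 1 has no unit code below region. Where a site reports that brand is set by unit and recorded incidence varies between units, brand-specific intervals from the named models are too narrow. The effect ranges from negligible to serious according to unit size, spread of incidence and brand concentration, none of which the documents give. The calculation is for a crude rate ratio; adjusting for covariates that explain part of the between-unit variation would reduce the effect. It should be addressed because it bears on the primary objective and is easiest to deal with before data are extracted.

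**What to change.** 1. In Annex 1, add an optional pseudonymised code for the unit that sets the brand (practice, municipality or institution), where the register holds it.
2. In Measure of effect, state that where a site reports that brand is set by unit, standard errors for brand-specific VE are cluster-robust on that unit. Name this one method for all sites. A unit stratum or random intercept is a different model, and leaving the choice open would work against harmonisation. Require a small-sample correction with fewer than about 30 units.
3. Where brand is set by region, cluster on the existing region field, with the same correction.
4. Carry these standard errors into the two-stage pooling.
5. Sites with only aggregated data and no unit code should report that their intervals assume independent subjects.

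The cost is one extra code per subject where it exists, a variance option in standard software, and wider intervals where clustering is present. Where brand is mixed within units and units are numerous, the intervals will hardly change.
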